2 STUDY OBJECTIVES

The overall objective of the study programme is to determine whether different signatures of immune status and/or corticosteroids biological activity influence the responses to hydrocortisone plus fludrocortisone of adults with sepsis. To this end, several predefined biomarker cohorts of patients will be randomly allocated to receive hydrocortisone plus fludrocortisone or their respective placebos with "primary objective" and "secondary oobjectives" defined below.

2.1 PRIMARY OBJECTIVES OF EACH ANALYSIS BY BIOLOGICAL MARKER

To compare the effect hydrocortisone plus fludrocortisone vs. placebo on a composite of death or persistent organ dysfunction – defined as continued dependency on mechanical ventilation, new renal replacement therapy, or vasopressors – assessed at 90 days on intensive care unit (ICU) adults and having different biological profiles for immune responses and corticosteroids bioactivity.

2.2 SECONDARY OBJECTIVES OF EACH ANALYSIS BY BIOLOGICAL MARKER

- To compare the effect of hydrocortisone plus fludrocortisone vs. placebo on:
 - 1) 6-month mortality;
 - 2) 6-month HRQoL;
 - 3) organ function (days 1, 2, 3, 4, 7, 10, 14, and 28 if in ICU);
 - 4) hyperglyceamia as defined by glucose levels of >8.3 mmol/L (150mg/dL) (daily up to day 28)
 - 5) hypernatremia as defined by serum sodium levels of >150mmol/L (daily up to day 28)
 - 6) secondary infection (daily up to day 90)
 - 7) beeding in the gastrointestinal tract defined by clinical evidence of active bleeding and need for blood transfusion OR hemostatic endoscopic or surgical procedures
 - 8) neurological cognitive dysfunction defined as by low score on the PROMIS Adult cognitive function score (appendix 15.4.7)
 - 9) neuromuscular weakness defined as a grade of 2 or more on Muscular Disability Rating Scale (MDRS) (appendix 15.4.6)

[figure not shown]

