Main objective and primary endpoint	To compare the effect hydrocortisone plus fludrocortisone vs. placebo on a composite of death or persistent organ dysfunction – defined as continued dependency on mechanical ventilation, new renal replacement therapy, or vasopressors – assessed at 90 days on intensive care unit (ICU) adults and having different biological profiles for immune responses and corticosteroids bioactivity The primary endpoint is death or persistent organ dysfunction (defined as continued dependency on mechanical ventilation, renal replacement therapy, or vasopressors) and with SOFA score >6 up to 90 days.						
Secondary objectives	 Mortality and health-related quality of life at 6 months; 						
and endpoints	 Daily organ function (SOFA score days 1, 2, 3, 4, 7, 10, 14, 28, and 90); 						
	 Daily secondary infections (up to 90 days) Daily blood and urinary levels of glucose, sodium and potassium (up to 28 day) Daily gastroduodenal bleeding (up to 28 day) Daily cognitive function and muscles' strength (days 1 to 28, 90 and 180 days) 						
Study design	Multi-arms Parallel blinded randomized controlled trial preceded						
	by a 6-month run-in observational period. Observational phase (run-in period) Interventional phase. 						
Inclusion Criteria	1. Patients ≥18 years old;						
observational phase: (N°1,2,3,4,6,7,8,9) interventional phase:	 Admitted to ICU with proven or suspected infection as the main diagnosis; Community acquired pneumonia related sepsis OR vasopressors dependency (norepinephrine, epinephrine, vasopressin, dopamine, phenylephrine) OR septic shock (Singer 2016: vasopressor to maintain mean blood pressure of at least 65 mmHg and lactate levels above 2 mmol/l) OR acute 						
(N°1,2,3,4,5,6,7,8).	 respiratory distress syndrome (ARDS – Ranieri 2012: a- acute onset, i.e. within one week of an apparent clinical insult and with progression of respiratory syndrome, b- bilateral opacities on chest imaging not explained by other pulmonary pathologies, e.g. pleural effusion, atelectasis, nodules etc, c-no evidence for heart failure or volume overload, d- PaO2/FiO2 ≤ 300 mm Hg, - PEEP ≥ 5 cm H2O Patient who has signed an informed and written consent whevener he/she is able of consent, if not, if not ascent from his/her representant whenever he/she is present at time of screening for inclusion 						

	5. Patients who have been tested for one or more RECORDS
	specific biomarkers:
	a. CIRCI
	b. Endocan
	c. GILZ
	d. CPD

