5.8 Table or diagram summarising the chronology of the study

							Da	ays						6 months
	0	1	2	3	4	5- 6	7	8- 9	10	11- 13	14	28	90	
Verification of inclusion and exclusion criteria	X													
Informed consent	Х													
Source of infection		х												
Severity of illness (SAPS II score)		x												
Sepsis data		х												
Pre-existing comorbidities (Charlson comorbidity index, Clinical Frailty Score)		x												
Randomization* (Interventional phase)		х												
Dispensation of treatments		X	X	Х	X	Х	Х							
Biological samples<	Х	Х	x	х	х	х	х	х	x	х	х	x		
Additional Biological samples (biomarqueurs)	X	Xa					X							
Protocol adherence ^b		х	Х	Х	Х	Х	Х							
Co-interventions ^c		Х	Х	х	х	Х	х	Х	х	х	Х	Х	х	
Death or persistent organ dysfunction ^d		х	x	x	х	х	x	х	х	х	x	х	х	x
Vasopressor dependency		х	x	x	х	х	x	х	х	х	x	Х	х	
Organ function including renal function (SOFA score)*	Х	x	x	X	X		X		x		X	x		
HRQoL (EQ-5D-5L) ^e , Promis		x										х	х	x
Serious adverse events*		x	Х	Х	Х	х	x	х	х	х	х	х	x	X

^aMust be collected before the first dose of investigational product. Samples include blood, urine, cells, exhaled air

^bReceipt of every planned dose according to schedule until completion of 7-day treatment protocol, samples collected per protocol instructions, biomarkers collected before the first dose of investigational product.

^cAdministration of mechanical ventilation, renal replacement, vasopressors, vitamin C, thiamine, intravenous fluids, blood products, sedatives, and antimicrobials. Daily data until ICU discharge or 28 days (whichever comes first).

^dDependency on mechanical ventilation, renal replacement, or vasopressors. eEQ5D to be filled at 3 and 6 months

* Interventional trial

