5.14 Outcome Measures

5.14.1 Primary Outcome

The primary outcome will be 90-Day organ dysfunction, ventilation and vasopressors free survival after randomization, which is a composite of day 90 mortality and survival free days off vasopressors and mechanical ventilation, and with SOFA score >6 (Laterre 2019). Such composite outcomes are increasingly used in ICU trials as reliable patient-centered outcomes (Kalkman 2015; Mehta 2017; Semler 2018).

Data on the vital status at day 90 after randomisation will be collected from the medical files (including electronic medical files for the entire hospital) and phone calls to patients and their designated contact persons. The primary endpoint is a binary variable. Patients will be classed as positive outcome if they are alive at day 90 and free of vasopressor therapy, mechanical ventilation and organ dysfunction. Patients

will be classed as negative outcome if they either died in the first 90 days after randomisation or if they remained vasopressor or mechanical ventilation dependent or with a SOFA score >6 beyond 28-days.

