5.14.2 Secondary Outcomes

The secondary outcomes will include:

1) Mortality at 7, 14, 28 day and 6 months.

2) Vasopressor free days: defined as the number of days with permanent hemodynamic stability in the absence of any vasopressor agent, norepinephrine, phenylephrine, epinephrine, dopamine, vasopressine or its analogs, and soever. When a patient will die on vasopressor therapy, the corresponding vasopressor free day will be 0.

3) Mechanical ventilation free days: defined as the number of days with permanent appropriate oxygenation while the patients is extubated and breathing spontaneously, i.e. no need for non invasive ventilation, high flow oxygen or CPAP. Other uses of non-invasive ventilation (e.g., chronic night-time use for chronic obstructive pulmonary disease) are not counted. When a patient will die on mechanical ventilation or will be discharge home on mechanical ventilation, the corresponding mechanical ventilation free day will be 0.

4) Organ dysfunction free days: Organ function (including renal function) will be assessed by the SOFA score (Vincent 1996). Organ dysfunction will be defined by a SOFA score of > 6 (Annane 2018). Organ dysfunction free days are defined by the number of days with os total SOFA score of 6 or less. When a patient will die on vasopressor therapy, the corresponding vasopressor free day will be 0.

5) HRQoL in 6-month survivors assessed by the EuroQol-5D (EQ-5D). This questionnaire is a standardised measure of health status developed to provide a simple, generic measure of health for clinical and economic appraisal. It is made up for two components; health state description and evaluation. The health status is measured in terms of five dimensions; mobility, self-care, usual activities, pain/discomfort, and anxiety/depression. In evaluation part, the respondents evaluate their overall health status using the visual analogue scale. See Figure 4.

6) Proportion of patients with a decision to withhold and/or withdraw active treatments

7) ICU and hospital length of stay

8) Rate of re-admission to the ICU during the 180 days after randomization

9) Safety endpoints:

- Proportion of patients affected by any serious adverse events associated with corticosteroids, among the following: hospital-acquired infections, hyperglycemia, hypernatremia, neurological disorders (coma, stroke or muscle weakness, as defined below) during the 90 days after randomization
- Coma will be defined as a Glasgow coma score < 8

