SOFA scores will be calculated from tests ordered locally. In case of missing data (i.e. if the necessary test is not done at certain study time points), SOFA scores will be imputed. All imputations will be prespecified in the statistical analysis plan before unblinding the trial.

Clinical (non-biomarker) data in this trial will be obtained from the patients' medical records. Local research teams will be responsible for data collection while the patients are still hospitalized.

In contrast, telephone follow-up at 90 day and at 6 months will be centralized and conducted by the URC Paris Saclay Ouest to 1) ensure uniform use of the follow-up questionnaires; and 2) reduce burden on local research teams.

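### The SOFA schedules disagree about day 90, and neither they nor the day-90 data list support the outcomes that use SOFA

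*Protocol*

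**What the plan says.** The protocol states when SOFA is taken in three places:

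- Study Summary, secondary objectives: "Daily organ function (SOFA score days 1, 2, 3, 4, 7, 10, 14, 28, and 90".
- Section 2.2, item 3: "organ function (days 1, 2, 3, 4, 7, 10, 14, and 28 if in ICU".
- Section 5.8, the row headed "Organ function including renal function (SOFA score": marked at days 0, 1, 2, 3, 4, 7, 10, 14 and 28, and blank at days 5-6, 8-9, 11-13, 90 and six months.

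Two outcomes depend on the score. In section 5.14.1 a patient fails on the primary outcome by dying or if they "remained vasopressor or mechanical ventilation dependent or with a SOFA score >6 beyond 28-days", and succeeds if "alive at day 90 and free of vasopressor therapy, mechanical ventilation and organ dysfunction". Section 5.14.2, item 4, sets organ dysfunction at a SOFA above 6 and adds: "Organ dysfunction free days are defined by the number of days with os total SOFA score of 6 or less". It gives no time horizon for that count.

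On data collection, sections 5.4 and 5.15 call for daily clinical and laboratory data until ICU discharge or day 90. Footnote c of the section 5.8 table stops co-intervention data at ICU discharge or day 28. Section 5.15 says that SOFA is calculated from locally ordered tests, and: "In case of missing data (i.e. if the necessary test is not done at certain study time points), SOFA scores will be imputed". The rules are left to the statistical analysis plan. The same section makes the day-90 telephone follow-up central.

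**The concern.** A site that follows section 2.2 and the section 5.8 table records no SOFA after day 28, yet the primary outcome asks for SOFA status after day 28 and at day 90. The table does mark the composite outcome at day 90, but footnote d defines it by ventilation, renal replacement or vasopressors. A correctly completed row therefore still captures no SOFA.

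At stake is how a day-90 survivor who is off organ support is classified. Without a stated rule the SOFA component could be dropped, imputed or assumed normal, and these choices can put the same patient in different classes. Section 3 expects no missing data for the primary outcome. A component with no visit in the table would be missing by design. The secondary day count has the same weakness, because most of its days carry no scheduled score.

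**Working it through.** The protocol gives no figure to reproduce here. The check is a count of scheduled days set against the days that the definitions need.

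**1. Scheduled SOFA days**

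| Place | Scored days within 1-28 | After day 28 |
|---|---|---|
| Study Summary | 1, 2, 3, 4, 7, 10, 14, 28 = 8 | day 90 |
| Section 2.2, item 3 | the same 8 | none |
| Section 5.8, SOFA row | the same 8 (plus day 0) | none |
| Sections 5.5 and 5.15, day-90 list | not applicable | SOFA not listed |

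Unscored days within days 1-28: 28 - 8 = 20. They are 5-6 (2), 8-9 (2), 11-13 (3) and 15-27 (13), and 2 + 2 + 3 + 13 = 20. Even on the Study Summary's schedule, the gap from day 28 to day 90 is 90 - 28 = 62 days.

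**2. What the gap allows.** Take a constructed patient with SOFA 8 on day 14 and 5 on day 28. From scheduled scores alone, organ-dysfunction-free days within days 15-28 lie between 1 (day 28 only) and 13 + 1 = 14. These are bounds, not an expected error, and daily ICU data would narrow them.

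**3. What the other data supply.** The SOFA addendum is listed but not reproduced, so I assume the usual six organ systems.

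| System | Daily ICU list (5.4, 5.15) | Day-90 list (5.5, 5.15) |
|---|---|---|
| Respiratory | arterial oxygen tension; FiO2 not listed | ventilation only |
| Coagulation | platelets | none |
| Liver | bilirubin | none |
| Circulation | blood pressure, vasopressors | vasopressors; blood pressure if in hospital |
| Nervous system | Glasgow score not listed | Glasgow score |
| Renal | creatinine | renal replacement only |

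The inputs are listed for 4 of 6 systems on ICU days and for 2 of 6 at day 90. After ICU discharge the daily list ends, and no passage gives a SOFA status. Between day 28 and day 90 even the ICU data are in doubt: sections 5.4 and 5.15 run to day 90, footnote c stops at day 28, and the table's biological-sample row also ends at day 28.

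**4. How many patients could be touched.** Section 9.1 plans on day-90 mortality of 45% against 35%, so survivors are 100 - 45 = 55% to 100 - 35 = 65%. This is a ceiling. Survivors still ventilated or on vasopressors fail without reference to SOFA. The rates also stand under the primary-outcome heading, although the primary outcome is a composite.

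**The case against.** The strongest reply is that the data mostly exist. Section 3 has site personnel document the composite at day 90, and section 5.15 makes local teams responsible while patients are in hospital. Sections 5.4 and 5.15 collect most components on every ICU day. The inpatients most likely to exceed a SOFA of 6 are therefore under site observation. Since SOFA is required on at least eight days, FiO2 and Glasgow score must be captured somewhere, so the daily list may not be the full case report form. Section 2.1 and footnote d state the composite without SOFA; if that version governs, the day-90 problem goes away. Imputation is deferred to the analysis plan, which is normal.

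Much of this stands, and it rules out several stronger readings that a reader might infer:

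- That SOFA is never taken at day 90. The Study Summary schedules it, so the fault is a contradiction.
- That SOFA is taken only in ICU. In section 2.2 the ICU qualifier may attach to day 28 alone, and the other two schedules carry no such limit.
- That the outcomes cannot be measured. Most components are available on ICU days.
- That nearly every survivor's score would be imputed, or that the error falls where the arms would differ. No passage supports either.

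What the reply does not answer is the mismatch itself. Section 5.14.1 includes SOFA, and sites are not told to record it when it is needed. The imputation sentence concerns tests not done at study time points. An analysis plan can set rules for missed tests, but it cannot supply values that were never scheduled.

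**Conclusion.** The point holds as an inconsistency between the SOFA schedules and the outcomes that use them. Two of the three schedules have no SOFA after day 28, while section 5.14.1 needs SOFA status after day 28 and at day 90. All three score 8 of days 1-28, while section 5.14.2 counts individual days. No SOFA status is defined after ICU discharge.

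The number of patients misclassified cannot be derived from the protocol; 55-65% is only the planned share of survivors. The primary-outcome part depends on a definition that includes SOFA. The day-count part does not. I rate this as something that should be fixed rather than a fatal flaw, because daily ICU data already cover much of the gap.

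**What to change.** 1. Reconcile the Study Summary, section 2.2, the section 5.8 table and section 5.14.1, first settling whether SOFA belongs in the primary outcome.
2. If it does, add a day-90 SOFA to section 2.2, to the SOFA row in section 5.8 and to the day-90 lists in sections 5.5 and 5.15, for patients still in ICU or on organ support.
3. Derive SOFA on each ICU day from the daily data, adding FiO2 and Glasgow score to the daily eCRF page, and align footnote c with the day-90 limit in sections 5.4 and 5.15.
4. State that patients discharged alive without organ support count as SOFA of 6 or less unless readmitted to ICU.

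The cost is one table row, matching edits to the lists, two fields normally charted in ICU and one scoring sentence. The small downside is that a discharged patient whose unmeasured SOFA exceeds 6 is scored as recovered.

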5.4 Follow-up visits

The patients included will be further followed for up to 180 days after randomization. Clinical and biological data will be assessed as described in table 4.1.19

Daily data until ICU discharge or 90 days (whichever comes first):

- a. Vital status
- b. protocol adherence (receipt of every planned dose until completion of 7 days treatment protocol),
- c. co-interventions (administration of mechanical ventilation, renal replacement, vasopressors, unblinded corticosteroids, thiamine, vitamin C, other vitamins, nutrition, intravenous fluids, blood products, anticoagulants, sedatives, stress ulcer prophylaxis, and antimicrobials),
- d. core temperature (lowest and highest of the day), vital signs (lowest and highest values for heart rate, systolic and diastolic blood pressure) and whenever needed central hemodynamic data (one per day),

standard laboratory data including serum and urinary electrolytes, creatinine, urea, cholesterol, triglycerides and glucose levels, arterial lactate levels, arterial oxygen tension and hemoglobin oxygen saturation, arterial pH, white blood cell counts, hemoglobin and hematocrit levels, INR, platelets count, total bilirubin levels.

- e. Sampling for microbiology or virology will be collected at Day 1, and 7, and additional sampling will be left at physicians' discretion
- f. Whole blood samples will be collected at Day 1 and Day 7 for measurements of biomarkers described in WP3 and WP4. These blood samples will be managed within WP2.

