- Neurologic sequelae will be assessed according to the score on the Muscular Disability Rating Scale (MDRS), with a score of 1 indicating no deficit, 2 minor deficit with no functional disability, 3 distal motor deficit, 4 mild-to-moderate proximal motor deficit, and 5 severe proximal motor deficit.
- Proportion of patients affected by hospital-acquired infections (CTINILS. Définition des infections associées aux soins. 2007)
- Number of episodes of hyperglycemia (blood glucose levels >150mg/dl) during ICU stay (or up to day 90, whichever occurs first)
- Number of episodes of hypernatremia (serum sodium > 145 mmol/L) during ICU stay (or up to day 90, whichever occurs first)
- Glasgow coma scale at ICU and hospital discharge (see annex).
- Number of patients with an episode of stroke (medical diagnosis as registered in the medical file) during ICU stay (or up to day 90, whichever occurs first)
- Gastroduodenal bleeding requiring transfusion or hemostatic treatment during ICU stay (or up to day 90, whichever occurs first)

RECORDS" protocol, version 4.0 of 03/03/2021

34/61

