5.15 Data Collection and Participant Follow-up

Potential participants will be referred to the research team by intensivists and other ICU staff. The research team will confirm eligibility and the site principal investigator and co-investigators will confirm whether the patient or others authorized persons may be approached for consent. If that is the case, the research team will obtain consent from the patient or others authorized persons or will enroll and obtain consent subsequently as a deferred consent model

Daily data will be collected from day 1 until day 90 (or at the time of ICU discharge). At 6 months, followup will be achieved by telephone by the Coordinating Centre. Table 5.1.8 describes requirements and procedures at each follow-up time point. All study outcomes (as defined in sections 8.1 and 8.2) will be documented on the electronic CRFs (eCRF).

Time points:

- 1) Baseline data:
 - a. patient demographics, source of infection, severity of illness (SAPS II and SOFA scores) (Le Gall 1993), pre-existing comorbidities as defined in the Charlson comorbidity index (Table 3) (Charlson 1994), Clinical Frailty Scale (Table 4) (Rockwood 2005; Bagshaw 2014; Muscedere 2017).
 - b. Core temperature, vital signs, central hemodynamic data (if available)
 - c. Standard laboratory data including serum and urinary electrolytes, creatinine, urea, *cholesterol*, *triglycerides* and glucose levels, arterial lactate levels, arterial oxygen tension and hemoglobin oxygen saturation, arterial pH, white blood cell counts, hemoglobin and hematocrit levels, INR, platelets count, total bilirubin levels.
 - d. Microbiology and virology, blood and any suspected soure of infection will be sampled, nasopharyngeal, bronchial or broncho-alveolar lavage fluids will be tested by PCR for SARS-CoV-2 and other respiratory viruses.
 - e. Synacthen test, i.e. blood sample for cortisol measurement immediately before and 30 and 60 minutes after 250µg intravenous bolus of corticotrophin.
 - f. Whole blood samples will be collected for measurements of biomarkers described in WP3 and WP4. These blood samples will be managed within WP2.
 - g. Interventions: mechanical ventilation, renal replacement, vasopressors, unblinded corticosteroids, thiamine, vitamin C, other vitamins, nutrition, intravenous fluids, blood products, anticoagulants, sedatives, stress ulcer prophylaxis, and antimicrobials),

2) Daily data until ICU discharge or 90 days (whichever comes first):

- a. Vital status

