- b. protocol adherence (receipt of every planned dose until completion of 7 days treatment protocol),
- c. co-interventions (administration of mechanical ventilation, renal replacement, vasopressors, unblinded corticosteroids, thiamine, vitamin C, other vitamins, nutrition, intravenous fluids, blood products, anticoagulants, sedatives, stress ulcer prophylaxis, and antimicrobials),
- d. core temperature (lowest and highest of the day), vital signs (lowest and highest values for heart rate, systolic and diastolic blood pressure) and whenever needed central hemodynamic data (one per day),
- e. standard laboratory data including serum and urinary electrolytes, creatinine, urea, cholesterol , triglycerides and glucose levels, arterial lactate levels, arterial oxygen tension and hemoglobin oxygen saturation, arterial pH, white blood cell counts, hemoglobin and hematocrit levels, INR, platelets count, total bilirubin levels.

- f. Sampling for microbiology and virology will be done at Day 1, Day 3 and Day 7, additional samples will be left at hysicians' discretion
- g. Whole blood samples will be collected at Day 1 and Day 7 for measurements of biomarkers described in WP3 and WP4. These blood samples will be managed within WP2.

3) At 90- and 180-day data:

- a. Vital status
- b. Location: still ICU (or date discharge), hospital ward (or date discharge), rehabilitation centre, long-term facility, home (date discharge to home)
- c. co-interventions: mechanical ventilation (or date weaned off), renal replacement (or date weaned off), vasopressors (or date weaned off)
- d. core temperature (lowest and highest of the day), vital signs (lowest and highest values for heart rate, systolic and diastolic blood pressure) if still at hospital
- e. Glasgow coma scale
- f. Cognitive function
- g. MDRS score
- h. HRQoL

To minimize patient discomfort and bedside teams' workload, study sample collection will coincide as much as possible with the routine drawing of blood ordered by the treating teams. Also, for the convenience of the patient, study samples of day 0, day 1 and day 7 may be collected at the same time of clinically requested samples happening during the same day. The study samples will be destroyed thereafter if the patient or his/her authorized persons does not consent to participate.

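### Infection is an outcome to day 90, but scheduled infection data stop at ICU discharge, so later infections rest on passive adverse event recording and the arm discharged sooner may be favoured

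*Protocol*

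**What the plan says.** **Outcome window.** The Study Summary has "Daily secondary infections (up to 90 days" and section 2.2 has "secondary infection (daily up to day 90". In 5.14.2 the composite safety endpoint includes hospital-acquired infections and ends "neurological disorders (coma, stroke or muscle weakness, as defined below) during the 90 days after randomization". The separate infection endpoint is "Proportion of patients affected by hospital-acquired infections (CTINILS. Définition des infections associées aux soins. 2007", with no limit to the ICU stay. The hyperglycaemia, hypernatraemia, stroke and gastroduodenal bleeding items in the same list are each limited to the ICU stay or day 90, whichever is first.

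**Scheduled collection.** Section 5.4 heads its list "Daily data until ICU discharge or 90 days (whichever comes first", and 5.15 says "Daily data will be collected from day 1 until day 90 (or at the time of ICU discharge". Microbiology and antimicrobials sit inside these daily lists. Footnote c to the schedule in 5.8 stops co-interventions, including antimicrobials, at ICU discharge or day 28. The day-90 and day-180 lists (5.5, 5.15) cover vital status, location, organ support, temperature and vital signs if still in hospital, coma scale, cognition, muscle score and quality of life. Infection is not among them.

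**Adverse event route.** Section 7.3.2 has the investigator record all adverse events, serious or not, in the eCRF. The serious adverse event row in 5.8 runs through day 90 to 6 months. Section 7.3.2.2 makes grade 4–5 infections and superinfections of grade 3 or more notifiable.

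**The concern.** Infection is among the harms that 5.14.2 itself associates with corticosteroids, so a comparison that understates it matters. While a patient is in ICU, there is a scheduled daily record from which an infection can be recognised and dated. After ICU discharge, the same outcome depends on someone reporting an adverse event. The switch between the two occurs at ICU discharge, which follows randomisation and which treatment may influence. ICU length of stay is a secondary outcome in 5.14.2, and 9.1 cites 17.1 v 15.0 vasopressor-free days in favour of hydrocortisone plus fludrocortisone. That makes earlier discharge in the treated arm plausible, though it is not evidence about ICU stay as such. If one arm leaves ICU sooner, its period of systematic ascertainment is shorter. A statistical analysis plan can choose an estimator but cannot recover infections that were never recorded.

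**Working it through.** The protocol states no figure for this point, so there is none to reproduce. The check has two parts.

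**1. Windows side by side**

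| Element | Where | Ends |
|---|---|---|
| Secondary infection outcome | Study Summary, 2.2 | Day 90 |
| Hospital-acquired infection in safety composite | 5.14.2 | Day 90 |
| Daily data, with microbiology and antimicrobials | 5.4, 5.15 | ICU discharge or day 90, whichever is first |
| Antimicrobials, schedule footnote | 5.8 | ICU discharge or day 28 |
| Day-90 and day-180 items | 5.5, 5.15 | No infection item |
| Adverse event recording in eCRF | 7.3.2 | No ICU limit stated |
| Notification to sponsor | 7.3.2.1 | Drug administration period |
| Notification to sponsor | 7.3.2.4 | Whole follow-up, and 90 days after treatment ends |
| Serious events that are trial outcomes | 7.3.2.3 | CRF only, not reported as SAEs |

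Between ICU discharge and day 90, no scheduled item feeds the infection outcome. What remains is event recording, and the last three rows do not agree with each other.

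**2. Possible size (illustration; all inputs assumed)**

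Assume the same constant infection hazard h per day in both arms, an exponential ICU stay with mean m days, and capture only in ICU. Then

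P(captured by day 90) = h/(h + 1/m) × [1 − exp(−(h + 1/m) × 90)].

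For h = 1% and m = 12: 0.01/(0.01 + 0.0833) = 0.107, and the bracket is practically 1. For m = 14: 0.01/(0.01 + 0.0714) = 0.123.

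| h per day | m = 12 | m = 14 | Difference (points) | Relative | p<0.05 at 900 per arm |
|---|---|---|---|---|---|
| 1% | 10.7% | 12.3% | 1.6 | 13% | 18% |
| 2% | 19.4% | 21.9% | 2.5 | 12% | 26% |
| 3% | 26.5% | 29.6% | 3.1 | 10% | 31% |

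The last column uses the maximum of 1800 patients at 1:1. The whole difference is spurious only if the ICU hazard continues unchanged to day 90, so that the true difference is nil.

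Now let risk after ICU apply only on the ward, with hazard w and a mean ward stay of 12 days in both arms. Part of the captured difference is then real, because fewer ICU days mean fewer infections. Ignoring the negligible day-90 truncation, the artefact is the captured difference × w/(w + 1/12). With h = 2% and ICU stays of 12 v 16 days:

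- Captured difference: 0.02/(0.02 + 1/16) − 0.02/(0.02 + 1/12) = 0.242 − 0.194 = 0.049, or 4.9 points.
- Artefact: 0, 0.3, 0.5 and 1.0 points for w = 0, 0.5, 1 and 2% per day.

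With equal ICU stays, the captured difference and the artefact are both zero.

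**The case against.** The strongest reply is that post-ICU infections are collected. All adverse events go into the eCRF, the serious event row runs to 6 months, 7.3.2.4 carries notification past ICU discharge, 5.15 has local teams collecting data while patients are in hospital, and the same section says all study outcomes are documented on the eCRF. This stands: a reader might infer that infection is collected only until ICU discharge, and the text does not support that. Limits on what is notified to the sponsor also do not limit what is recorded.

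It is also fair that the daily ICU lists name no infection event, only microbiology and antimicrobials, so the lists are not exhaustive of outcomes. But those items give a systematic basis for identifying infection in ICU, and nothing equivalent is scheduled afterwards. The argument is about unequal intensity of ascertainment, not absence of data.

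Three further inferences fail:

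- That the faster arm will show fewer infections by design. This needs a difference in ICU stay and incomplete capture later, and a true excess of infections on corticosteroids could offset it.
- That infections fall by 14% (12/14 − 1). That is a ratio of days at risk and suits a count; the 5.14.2 endpoint is a proportion of patients.
- That only 13 to 16% of the window is observed (12/90, 14/90). This counts days at home as time at risk of hospital-acquired infection and ignores event recording.

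Sections 5.4 and 5.15 also differ on sampling: "Sampling for microbiology or virology will be collected at Day 1, and 7" against "Sampling for microbiology and virology will be done at Day 1, Day 3 and Day 7". This is a real but separate and minor inconsistency. It falls in the first week, applies to both blinded arms, and does not cause between-arm bias.

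**Conclusion.** The mismatch is in the text: the infection outcome runs to day 90, while scheduled infection-related data end at ICU discharge and no later item picks infection up. Ascertainment is therefore systematic in ICU and passive afterwards, with contradictory statements about notification. The comparison may be biased in favour of the arm discharged sooner.

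Under assumed ICU stays of 12 v 14 days, a 1 to 3% daily hazard unchanged after ICU, and no capture after ICU, the bias is 1.6 to 3.1 points, about 10 to 13% relative. These are unfavourable assumptions. Any post-ICU capture reduces the bias, a low ward risk makes it small, and equal ICU stays remove it. The protocol does not supply the inputs needed to say which case applies, so this is a risk and not a demonstrated bias. It is still worth correcting, because it concerns a key harm and the lost data could not be recovered at analysis.

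**What to change.** Either of two changes closes the gap:

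- Add one item to the day-90 data in 5.5 and 5.15: hospital-acquired infection since ICU discharge, yes or no, with date. The sources are already in use at day 90: hospital records and telephone calls for vital status (5.14.1), and the central telephone follow-up (5.15). The cost is one extra eCRF item and a small data-entry burden.
- Or restate the outcome in the Study Summary, 2.2 and 5.14.2 as ICU-acquired infection, with ICU discharge and death treated as competing events. The cost is a change of wording and a narrower question.

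In either case, reconcile 7.3.2.1, 7.3.2.3 and 7.3.2.4, together with the list in 7.3.2.2, so that the period and route for infections after ICU discharge are stated once. Separately, make the microbiology sampling days in 5.4 and 5.15 agree.
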